To assess the effect of Ad26.COV2.S on all molecularly confirmed ^a symptomatic COVID-19 ^{b,c} , as compared to placebo	
 Burden of disease (BOD) endpoint^f derived from the first occurrence of molecularly confirmed^a symptomatic COVID-19^{b,c} (meeting the mild, moderate or severe/critical COVID-19 case definition) with onset at least 14 days after double-blind vaccination (Day 15). BOD endpoint^f derived from the first occurrence of molecularly confirmed^a symptomatic COVID-19^{b,c} (meeting the mild, moderate or severe/critical COVID-19 case definition) with onset at least 28 days after double-blind vaccination (Day 29).

To assess the effect of Ad26.COV2.S on occurrence of confirmed asymptomatic or undetected infections with SARS-CoV-2, as compared to placebo	
 • Serologic conversions between baseline (Day 1; pre-vaccination) and Day 29, between Day 29 and Day 71, between Day 71 and Month 6/unblinding visit, and 18 months after double-blind vaccination (approximately 12 months after initiation of the open-label phase of the study) using an enzyme-linked immunosorbent assay (ELISA) and/or SARS-CoV-2 immunoglobulin assay that is dependent on the SARS-CoV-2 nucleocapsid (N) protein • Asymptomatic infection detected by RT-PCR at the time of the Month 6/unblinding visit
To assess the efficacy of Ad26.COV2.S in the prevention of SARS-CoV-2 infection (both symptomatic and asymptomatic infections combined, that are serologically and/or molecularly confirmed ^a), as compared to placebo	First occurrence of SARS-CoV-2 infection (serologically and/or molecularly confirmed ^a) with onset at least 28 days after double-blind vaccination (Day 29)
Safety	
To evaluate safety in terms of serious adverse events and adverse events of special interest (SAEs and AESIs; during the entire study), medically-attended adverse events (MAAEs; until 6 months after double-blind or open-label vaccination), and MAAEs leading to study discontinuation (during the entire study) for all participants	Occurrence and relationship of SAEs and AESIs (during the entire study), MAAEs (until 6 months after double-blind or open-label Ad26.COV.S), and MAAEs leading to study discontinuation (during the entire study) for all participants following vaccination

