3.5.3. Asymptomatic infections and all infections (including asymptomatic)

Based on assumptions prior to unblinding the cases in the placebo group were assumed to be distributed as follows: 45% asymptomatic cases and 55% symptomatic cases of which 20% were mild infections, and 60% were moderate and 20% were severe infections, according to the case definitions. Based on a VE as detailed in [Table 4](#), events were simulated according to a binomial distribution and the primary endpoints evaluated against the SPRT boundary.

Upon crossing the SPRT boundary, the power against asymptomatic or undetected infections as well as against the evaluation of all infections was calculated (null hypothesis $VE>0$). The alpha level for that evaluation was adjusted according to the procedure detailed in the statistical hypothesis evaluation.

The results are based on 1000 simulations. The powers presented are not conditional on passing the first 2 secondary hypotheses.

Table 4 Powers for Asymptomatic and All Infections for various Fractions of available N-Elisa samples at 2.5 months at the time of analysis

Fraction of available N-Elisa samples At 2.5 months	Vaccine efficacy			Power		
	Moderate/Severe	Mild	Asymptomatic	Moderate/Severe	Asymptomatic	All infections
100%	70%	60%	30%	99%	14%	96%
100%	70%	60%	40%	99%	28%	99%
100%	70%	60%	50%	99%	47%	>99%
50%	70%	60%	30%	99%	4%	99%
50%	70%	60%	40%	99%	7%	>99%
50%	70%	60%	50%	99%	13%	>99%

This is based on the protocol assumed incidence of 1.4% during 3 months and waning thereafter (by 50% in Month 4, by 62% in Month 5 and beyond) and a sample size of 60,000.

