5.2.5.2. Classification

As for symptomatic COVID-19 case classification, a similar approach will be taken to identify asymptomatic infections or undetected cases via an algorithmic approach. Cases will then be reviewed and classified as being an "Asymptomatic SARS-CoV-2 infection" by the Clinical Severity Adjudication Committee.

Relevant definitions for programmed algorithm:

Identification of potential asymptomatic SARS-CoV-2 infections via PCR: in the event of a positive PCR, the cases will be reviewed for the presence of signs and/or symptoms of COVID-19 since baseline employing the definitions of onset and resolution of section 5.2.2. In the absence of signs and/or symptoms, the case will be classified per algorithm as asymptomatic.

Identification of potential asymptomatic or undetected SARS-CoV-2 infections through seroconversion:

- **SARS-CoV-2 seroconversion with onset Day >28** is based on the available data from Day 71, Month 6 and/or unblinding visit. If positive at any timepoint while the subject was seronegative at baseline (and at Day 29 for the PP analysis after day 28), a subject is considered seroconverted. If Day 29 is missing or not available, then the subject is considered negative on that Day.
- **SARS-CoV-2 seroconversion from Day 1 to Day 29**, is based on the available data on day 29. If positive at day 29 while the subject was seronegative at baseline or missing, a subject is considered seroconverted between day 1 and day 29.

- A **seroconverted participant** is a subject with serological conversion without an earlier molecularly confirmed (SARS-CoV-2 positive RT-PCR or molecular test result from any available respiratory tract sample)

Upon algorithmic identification, cases will be evaluated as being an "Asymptomatic SARS-CoV-2 infection" by the Clinical Severity Adjudication Committee as follows:

- Asymptomatic SARS-CoV-2 infections or seroconverted participants as assigned via the programmed algorithm will be reviewed for the presence of possible COVID-19 signs and symptoms since baseline up to 7 days prior to the first positive PCR or up to the day of the first positive serology test.
- If no presence of signs/symptoms, the algorithm will be accepted and no further review by the CSAC and the case classified as Asymptomatic SARS-CoV-2 infections .
- If at least one sign or symptom present, those cases will be sent to the CSAC for review for a possible undetected symptomatic COVID-19.

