 - If reviewed by the CSAC as asymptomatic sars-cov-2 infections, cases will be classified as asymptomatic infections.
 - Seroconverted cases reviewed by the CSAC as symptomatic will be classified as **serologically confirmed COVID-19** and evaluated according to the accepted/reviewed severity and onset date.
 - PCR+ cases reviewed by the CSAC as symptomatic will be classified and evaluated according to the accepted/reviewed severity and onset date

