To assess potential time-effects of VE for secondary endpoints the following graphical explorations will be conducted. First, the Kaplan-Meier method will be used to plot the estimated cumulative incidence rates over time for the vaccine and placebo groups. This method will be used to estimate cumulative VE over time, defined as $[(1 \text{ minus ratio (vaccine/placebo)}) \text{ of cumulative incidence by time } t] \times 100\%$ with the method of Parzen, Wei and Ying applied to estimate pointwise and simultaneous $(1 - \alpha) \times 100\%$ CIs. Secondly, the method of Gilbert et al. (2002) will be used to evaluate VE over time based on the ratio of the smoothed instantaneous hazard in the vaccine and the placebo arm. More specifically, graphs will be created with $[(1 \text{ minus ratio (vaccine/placebo)}) \text{ of smoothed instantaneous hazard by time } t] \times 100\%$ and accompanying pointwise and simultaneous $(1 - \alpha) \times 100\%$ CIs over time since vaccination.

Any subgroup analysis for VE will be visualized as well with forest plots.

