5.5.2. Key Confirmatory Secondary Endpoint(s) and Estimand(s)

5.5.2.1. Definition of Endpoint(s)

Endpoint Label	Endpoint definition
Any symptomatic infection (BOD)	
For all subjects with a symptomatic, molecularly confirmed COVID-19 episode, classification based on any severity will be included.
 
Weight-adjusted analysis for severe disease will be done as follows. Any case of mild or moderate COVID-19 will be given a score of 1, severe/critical COVID-19 cases will be given a score of 2.
 
Subjects without a symptomatic, molecularly confirmed COVID-19 episode are implicitly categorized as 0.

Asymptomatic infection	
Asymptomatic infection with an onset at least 28 days after vaccination is considered as a subject with either serologic conversion (day 71 or month 6) or with a SARS-CoV-2 positive RT-PCR or molecular test result from any available respiratory tract sample (eg, nasal swab sample, sputum sample, throat swab sample, saliva sample) or other sample but both without a previous suspected, symptomatic COVID-19 episode according to the adjudication committee (asymptomatic as defined in section 5.2.5). Additionally, both types of asymptomatic infections will be analyzed separately as well (based on PCR versus based on serology).

	
Supportive endpoints:
 
 1. Seroconverted participants will be defined as participants with a serologic conversion (day 71 or Month 6 and/or unblinding visit) and without a previous SARS-CoV-2 positive RT-PCR or molecular test result from any available respiratory tract sample (eg, nasal swab sample, sputum sample, throat swab sample, saliva sample) or other sample regardless of prior symptoms 2. Subset of asymptomatic infections based on PCR results from the Month 6 and/or unblinding visit 3. Asymptomatic infections between Day 1 and Day 29 will also be analyzed as a supportive endpoint. If positive at Day 29, while the subject was seronegative at baseline, a subject is considered seroconverted.
All infections (Any SARS-CoV-2 Infection)	First occurrence of SARS-CoV-2 infection (serologically, including serologically symptomatic confirmed, and/or molecularly confirmed ^a) with onset at least 28 days after double-blind vaccination with study vaccine.

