For cases, the follow-up time is defined as the time between double-blind vaccination and the time of onset of infection (timepoint of a positive N-protein Elisa for asymptomatic subjects).

For supportive endpoints, Vaccine efficacy will be estimated with a 95% confidence intervals (as described in appendix 8).

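### SAP 5.5.1 orders VE-over-time curves for secondary endpoints without exempting those dated by scheduled serology, so the any-infection curve can show a false fall at Day 71

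*SAP*

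**What the plan says.** Section 5.5.1 introduces two displays with "To assess potential time-effects of VE for secondary endpoints the following graphical explorations will be conducted": cumulative VE from Kaplan-Meier incidence, and VE from the ratio of smoothed instantaneous hazards over time since vaccination. Both come with pointwise and simultaneous confidence intervals. No endpoint is excluded.

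Section 5.5.2.1 lists asymptomatic infection and any SARS-CoV-2 infection among the key confirmatory secondary endpoints. The latter is defined as "First occurrence of SARS-CoV-2 infection (serologically, including serologically symptomatic confirmed, and/or molecularly confirmed", so it mixes two kinds of event.

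The two kinds are dated differently:
- Asymptomatic serologic cases: section 5.5.4.3 takes the "timepoint of a positive N-protein Elisa for asymptomatic subjects". Section 5.2.5.2 says that seroconversion after Day 28 "is based on the available data from Day 71, Month 6 and/or unblinding visit".
- Symptomatic cases: dated at onset. Seroconverters whom the adjudication committee (CSAC) judges symptomatic are reclassified "and evaluated according to the accepted/reviewed severity and onset date" (section 5.2.5.2), so they are not dated at the draw.

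Section 5.5.4.3 does not repeat the curves. It asks for the proportion who seroconverted at each available timepoint, by group. Neither section gives a rule for interval censoring.

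**The concern.** An asymptomatic seroconversion found at Day 71 may have occurred on any day since the Day 29 sample. If it is plotted at the draw date, the any-infection curve holds mostly symptomatic cases from Day 29 to Day 70. It then takes in six weeks of asymptomatic infections at once. When the vaccine protects less against asymptomatic infection, that change in case mix looks like a loss of efficacy on a particular day.

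The stated purpose of the displays is to look for time-effects of VE, and section 5.4.6 shows that the plan takes possible waning seriously. The confidence intervals around the curve describe sampling error and say nothing about the dating rule, so they would not warn the reader. For asymptomatic infection alone, constant VE gives no false fall, but the curve has almost no time resolution and mainly reproduces the visit calendar.

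**Working it through.** The SAP gives no figure for these curves, so there is none to reproduce. The check uses its planning inputs.

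**Inputs from section 3.5.3 and Table 4**
- Placebo case mix: "45% asymptomatic cases and 55% symptomatic cases of which 20% were mild infections", with 60% moderate and 20% severe. The last three are read as shares of symptomatic cases, since they sum to 100%.
- VE: 70% moderate/severe, 60% mild, and 30%, 40% or 50% asymptomatic.

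**Assumptions added here**
- Rare events, constant incidence, and constant VE within each type.
- Every participant is sampled at Day 71.
- Base case: no asymptomatic infection is dated by PCR.

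**Symptomatic VE**
1 − (0.20 × 0.40 + 0.80 × 0.30) = 1 − 0.32 = 68%.

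**Correctly dated any-infection VE (flat over time)**
0.55 × 68% + 0.45 × VEa = 50.9%, 55.4% or 59.9% for VEa = 30%, 40% or 50%.

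**Draw-dated cumulative VE**
VE(t) = [0.55·S·0.68 + 0.45·A·VEa] / [0.55·S + 0.45·A]. Here S = t − 28 is the days of symptomatic accrual. A is the days of asymptomatic infection already revealed by a draw: 0 before Day 71, then 42.

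- To Day 70: A = 0, so the curve reads 68.0% whatever VEa is.
- Day 71: S = 43, so 0.55·S = 23.65 and 0.45·A = 18.9.
  - VEa 30%: (16.082 + 5.67)/42.55 = 51.1%
  - VEa 40%: (16.082 + 7.56)/42.55 = 55.6%
  - VEa 50%: (16.082 + 9.45)/42.55 = 60.0%
- The falls are therefore about 17, 12 and 8 points.
- With no further draw, the curve climbs back to 56.9%, 59.8% or 62.7% by Day 111 (S = 83).

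**If some asymptomatic infections are PCR-dated (assumed 10% to 30%)**

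| VEa | PCR share | Day 70 | Day 71 |
|---|---|---|---|
| 30% | 10% | 65.1% | 51.1% |
| 30% | 30% | 60.5% | 51.1% |
| 50% | 10% | 66.6% | 60.0% |
| 50% | 30% | 64.5% | 60.0% |

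The fall is then about 9 to 14 points at VEa 30% and about 4.5 to 7 points at VEa 50%.

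**After Day 71, with participant-specific unblinding**
Assume unblinding spread evenly over Days 84 to 140. The daily asymptomatic increment is proportional to (t − 71) × (fraction unblinded that day)/(fraction still blinded). There is no second step but a late slide:
- VEa 30%: 54.2% at Day 100, 51.3% at Day 125, 41.4% at Day 140.
- VEa 50%: 61.4%, 60.0% and 55.3% on the same days.

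The end points lie below the correct 50.9% and 59.9%. Detection coincides with censoring, so late draws weigh heavily on a shrinking risk set.

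**Smoothed hazard (assumed Epanechnikov kernel)**
- 14-day bandwidth: 68% at Day 57, 43% (VEa 30%) or 56% (VEa 50%) at Day 71, and 68% again at Day 85.
- 28-day bandwidth, VEa 30%: a broader fall, from 63% at Day 45 to 50% at Day 71.

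**Counter-check**
With VEa = 68%, equal to symptomatic VE, the curve stays at 68% throughout. With VEa = 80% it rises at Day 71: (16.082 + 15.12)/42.55 = 73.3%.

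**The case against.** The strongest objection is about scope. Section 5.5.1 opens with molecularly confirmed COVID-19 and lists graphs by severity, for the FDA definition and for medical intervention, not for infection endpoints. Section 5.5.4.1 then repeats both curves for severe disease and 5.5.4.2 repeats the Kaplan-Meier curve for any symptomatic infection. Section 5.5.4.3 repeats neither and uses visit-based proportions. The curves may never have been meant for infection endpoints. A reader might infer that the plan orders them for every secondary endpoint by name, but it does not. What stands is that the wording is unrestricted, that two serology-based endpoints fall under it, and that section 5.5.5 names a subset when the plan wants one.

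Four further inferences are tempting and not supported:
- That constant VE over time is enough to produce the fall. It also needs asymptomatic VE below symptomatic VE. Table 4 holds power scenarios set before unblinding, not findings.
- That every seroconversion lands on a draw date. Those judged symptomatic carry the reviewed onset date, and PCR-detected asymptomatic cases need not wait for a serology draw.
- That there is a second sharp drop at unblinding. Section 5.1.4 makes that visit each participant's own censoring date, and Day 112 is only an approximate median follow-up.
- That confirmatory conclusions are at risk. Those tests use the Appendix 8 estimate and its interval, not these curves.

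The plan also tabulates infections by type, analyses PCR-based and serology-based asymptomatic infections separately, and shows symptomatic-only curves. A careful reader could use these to detect the change in mix. They lessen the risk but do not correct the display.

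**Conclusion.** The point holds as a minor one. Taken literally, section 5.5.1 produces an any-infection VE curve that mixes onset-dated and visit-dated events, with no rule for interval censoring. Under the SAP's planning mix, cumulative VE falls falsely at Day 71 by about 17, 12 or 8 points for asymptomatic VE of 30%, 40% or 50%, followed later by a gradual slide as participants are unblinded.

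These sizes rest on the Table 4 values, constant incidence and full sampling at Day 71. They shrink if some asymptomatic infections are PCR-dated. The slide and the hazard figures also depend on the assumed unblinding spread, kernel and bandwidth. The consequence is limited to interpreting an exploratory display: a schedule artefact could be taken for waning.

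**What to change.** In section 5.5.1, limit the Kaplan-Meier and smoothed-hazard VE-over-time curves to endpoints whose onset is dated by symptoms or PCR.

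For any infection and asymptomatic infection, show VE per serology interval, using those that section 1.1 already defines ("between Day 29 and Day 71, between Day 71 and Month 6/unblinding visit"), or an interval-censored estimate. Count PCR-confirmed cases in the interval in which they occur, whether or not a later serology sample exists. Requiring an end-of-interval sample from everyone would drop confirmed cases and condition on post-randomization sample availability.

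The cost is SAP wording and one replaced display, with no new data. Time resolution is coarser, but that is what the draw schedule supports. The serologic part still depends on who was sampled, so sample availability should be shown by arm and interval.

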5.5.2. Key Confirmatory Secondary Endpoint(s) and Estimand(s)

5.5.2.1. Definition of Endpoint(s)

Endpoint Label	Endpoint definition
Any symptomatic infection (BOD)	
For all subjects with a symptomatic, molecularly confirmed COVID-19 episode, classification based on any severity will be included.
 
Weight-adjusted analysis for severe disease will be done as follows. Any case of mild or moderate COVID-19 will be given a score of 1, severe/critical COVID-19 cases will be given a score of 2.
 
Subjects without a symptomatic, molecularly confirmed COVID-19 episode are implicitly categorized as 0.

Asymptomatic infection	
Asymptomatic infection with an onset at least 28 days after vaccination is considered as a subject with either serologic conversion (day 71 or month 6) or with a SARS-CoV-2 positive RT-PCR or molecular test result from any available respiratory tract sample (eg, nasal swab sample, sputum sample, throat swab sample, saliva sample) or other sample but both without a previous suspected, symptomatic COVID-19 episode according to the adjudication committee (asymptomatic as defined in section 5.2.5). Additionally, both types of asymptomatic infections will be analyzed separately as well (based on PCR versus based on serology).

	
Supportive endpoints:
 
 1. Seroconverted participants will be defined as participants with a serologic conversion (day 71 or Month 6 and/or unblinding visit) and without a previous SARS-CoV-2 positive RT-PCR or molecular test result from any available respiratory tract sample (eg, nasal swab sample, sputum sample, throat swab sample, saliva sample) or other sample regardless of prior symptoms 2. Subset of asymptomatic infections based on PCR results from the Month 6 and/or unblinding visit 3. Asymptomatic infections between Day 1 and Day 29 will also be analyzed as a supportive endpoint. If positive at Day 29, while the subject was seronegative at baseline, a subject is considered seroconverted.
All infections (Any SARS-CoV-2 Infection)	First occurrence of SARS-CoV-2 infection (serologically, including serologically symptomatic confirmed, and/or molecularly confirmed ^a) with onset at least 28 days after double-blind vaccination with study vaccine.
Severe/critical infection	A subject is considered as an event when the first occurrence of molecularly confirmed COVID-19 case meeting severe/critical definition with onset at least 14 days and at least 28 days post double-blind vaccination.
COVID-19 requiring Medical intervention	
COVID-19 events requiring medical intervention including hospitalization based on objective findings such as ICU admission, mechanical ventilation, ECMO, decreased oxygenation, X-ray, CT findings, use of supportive medications or clinical course following adjudication by the CSAC with onset at least 14 days and at least 28 days post double-blind vaccination
 
The evaluation whether the endpoint is linked to objective measures will be done through the adjudication committee using all available information.
 
In addition, an algorithmic interpretation will be done, based on the MRU questionnaire only for consistency with the primary analysis.

The confirmatory estimands therefore are

Population: Prior SARS-CoV-2-uninfected, adults ≥ 18 years with or without comorbidities for COVID-19

Endpoint: as defined above.

Interventions: Ad26.COV2.S 5×10^{10} virus particles and placebo

Summary Measure: Vaccine Efficacy: $100 \times (1 - \text{ratio of endpoint mean vaccine/placebo})\%$

Intercurrent Events: /

Data handling for estimator: Subjects with major protocol deviations potentially impacting efficacy will be excluded from the analysis. Subjects with a positive serology test at baseline will be excluded from the analysis.

For the secondary endpoints all available cases at the time of data base cut off will be included in the analysis according to the pre-specified analysis population and time window for endpoint calculation.

The populations for analysis for the secondary endpoints are presented in [Table 8](#).

Table 8 Key confirmatory secondary endpoints and analysis set evaluations

	Key analysis population for evaluation of the statistical hypothesis	Supportive analysis set
Any symptomatic infection (BOD)	Per-Protocol analysis set baseline-Sero-Negative subjects with onset of infection at least 14 days and at least 28 days post double-blind vaccination	PP, SN/SP, Day 28* FAS, SN, Day 1 FAS, SN/SP, Day 1*
Any SARS-CoV-2 infection	Per-Protocol analysis set Sero-Negative subjects with onset of infection at least 28 day post double-blind vaccination	FAS, SN, Day 1 FAS, SN/SP, Day 1* PP, SN/SP, Day 28
Severe infection	Per-Protocol analysis set Sero-Negative subjects with onset of infection at least 14 and at least 28 days post double-blind vaccination	PP, SN/SP, Day 28* FAS, SN, Day 1 FAS, SN/SP, Day 1*
Medical intervention	Per-Protocol analysis set Sero-Negative subjects with onset of infection at least 14 and at least 28 days post double-blind vaccination	PP, SN/SP, Day 28* FAS, SN, Day 1 FAS, SN/SP, Day 1*
Asymptomatic or undetected infection	Per-Protocol analysis set Sero-Negative subjects with onset at least 28 days post double-blind vaccination	FAS, SN Day 1
Asymptomatic or undetected infection from Day 1 to Day 29	FAS, SN Day 1	
PP=per-protocol, SN=sero-negative subjects, Day 1/28=including infections with onset 1 day/28 days post double-blind vaccination, SP=seropositive subjects, FAS=full analysis set		

(*Any analysis regardless of serostatus will be done only if 7 or more events observed in the group of subjects who were seropositive at baseline.

